# 7.2 Benefits

- 7.2.1 The investigational device being used in this study may help straighten the subject's teeth or improve their smile. While there are no guarantees the study of this product will provide a conclusive outcome.
- 7.2.2 One benefit of the reduced wear time aligner therapy is aesthetics. Subjects are able to wear the aligners during periods when they are sleeping or otherwise at home; offering a more discrete option of therapy.
- 7.2.3 Another benefit of the reduced wear time aligner therapy is increased subject ease of using the device. Aligners must be removed prior to eating and drinking anything except cool water. The subject must also brush their

teeth prior to reinserting the aligners. If the aligners are only worn during sleep or times when the subject is not eating or drinking for a continuous 10-12 hours, subjects do not need to worry about this additional device/oral hygiene process.

7.2.4 Information from this study might help researchers develop a better orthodontic device that will help others in the future.

# 8. STUDY PROCEDURES

## 8.1 Screening

- 8.1.1 Subjects seeking orthodontic treatment will be screened through the Byte+ network of dental providers. Subjects who opt to receive orthodontic aligner treatment using the Byte® system will be screened for eligibility by the Investigator in the dental office. Screening will be based on potential study subject case complexity and eligibility.
- 8.1.2 Subjects will visit one of the Byte+ network dentists for an initial intraoral scan, x-ray (PAN, CBCT, CEPH and/or FMX), intraoral and extraoral photographs. An X-ray taken within a year from study visit may be used for treatment planning if deemed adequate by the Investigator.
- 8.1.3 Subjects will be screened based on the inclusion and exclusion criteria defined above.
- 8.1.4 Subjects will be informed that the investigational device is being studied for its safety and efficacy in achieving prescribed tooth movement per each individual subject's subject treatment plan and is not currently cleared by the FDA.
- 8.1.5 Informed consent (and parental consent for minors under the age of 18) will be obtained from the subject.

**CONFIDENTIAL:** The information in this study protocol is strictly confidential and is available for review to Investigators, study center personnel, the ethics committee, and the health authorities. It will not be disclosed to third parties without written authorization from the Sponsor, except to obtain informed consent from persons receiving the study treatment. Once the protocol is signed, its terms are binding for all parties.

- 8.1.6 All subjects screened will be documented in the Screening Log maintained at each investigational site.
- 8.1.7 Once the treatment plan is created, the Byte+ account manager will ensure that the subject's prescribed tooth movements are within the constraints and criteria outlined within this study's inclusion/exclusion criteria.
  - If the subject requires movements outside of the study's eligibility criteria, they can continue with their orthodontic treatment with Daytime aligners outside of the confines of this clinical study. In these cases, the Investigator will be informed by the digital lab as to why the subject is not eligible for the study; the Investigator in turn shall notify the subject and withdraw them from the study.

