# 2.2 Rationale:

- 2.2.1 Nighttime Aligners program smaller incremental tooth movements into each aligner tray/stage allowing for activation of biological cascade governing orthodontic tooth movement (Krishnan 2006, Kumasako-Haga 2019), with an added advantage of intermittent force resulting in reduced root resorption (Ozkalavci 2018). Movements of molar teeth and extrusive tooth movements are not eligible in the treatment plans for these aligners.
- 2.2.2 This clinical study is designed to provide Straight Smile (doing business as Byte) and Dentsply Sirona data to support performance, efficacy and safety of wearing Nighttime Aligners for 10-12 continuous hours per day (or night). The expressed movements demonstrated by the Nighttime Aligners (investigational/test group) will be compared to the expressed movements demonstrated by the Daytime Aligners (control group), which are worn for 20-22-hours per day. Both control and investigational groups are for subjects with mild malocclusion.
- 2.2.3 This clinical study involves no more than minimal risk (as defined in 21 CFR 50.3(k) or 56.102(i)) to the subjects. Based on this assessment, the IRB will be asked to make a determination that the clinical study does not pose more than minimal risk to the study subjects (non-significant risk) and thus the clinical study is considered to have abbreviated IDE requirements and does not require FDA approval of the study (21 CFR 8.12.2(b)).
  - This request is made in part by reviewing the recommendations provided by the Office of Good Clinical Practice, Office of Special Medical Programs, Office of the Commissioner Food and Drug US FDA in the document "Information Sheet Guidance for IRBs, Clinical Investigators, and Sponsors: Significant Risk and Non-significant Risk Medical Device Studies".

(https://www.fda.gov/regulatory-information/search-fda-guidance-documents/significant-risk-and-nonsignificant-risk-medical-device-studies)

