# Tooth movement treatment planning constraints of Nighttime Aligners (investigational):

Movement Type	Translate [B/L] (mm)	Torque / Incline (°)	Tip (°)	Rotate (°)	Intrude (mm)	Extrude (mm)
Per aligner	0.25 mm	1 °	1 °	1.6 °	0.1 mm	N/A
Tooth	Totals per treatment plan					
Incisors	5	25	25	45	2.5	N/A
Laterals	5	25	25	45	2.5	N/A
Canines	3	25	25	35	2.5	N/A
Premolars	2	10	10	10	1	N/A
Molars*	N/A	N/A	N/A	N/A	N/A	N/A

\*Movements of molar teeth are not in the treatment plans for these aligners.

6.1.3 Daytime Aligners are indicated for the treatment of tooth malocclusion in subjects with permanent dentition (i.e., second molars). The aligner system positions teeth by way of continuous gentle force. These aligners are to be worn by the subject 20-22 hours per day and night; aligners may be removed for small periods of time while eating, drinking or brushing.

Subjects will wear each aligner tray for 1-2 weeks, or as instructed by their dentist. When worn while sleeping, the therapy complements the circadian rhythm of bone remodeling and metabolism for tooth movement. Smaller incremental tooth movements are programmed into each aligner tray/stage allowing for activation of biological cascade governing orthodontic tooth movement, with an added advantage of intermittent force resulting in reduced root resorption. Daytime aligners (control) are made with material that is 0.30-0.35 inch thick and the planned tooth movement rate is 20% more than that of the Nighttime Aligners (investigational).

Tooth	movement	treatment	planning	constraints	of	Daytime	Aligners
(contro	ol):						

Movement Type	Translate [B/L] (mm)	Torque / Incline (°)	Tip (°)	Rotate (°)	Intrude (mm)	Extrude* (mm)
Per aligner	0.3 mm	1 °	1 °	2 °	0.1 mm	N/A
Tooth	Totals per treatment plan					
Incisors	5	25	25	45	2.5	N/A
Laterals	5	25	25	45	2.5	N/A
Canines	3	25	25	35	2.5	N/A
Premolars	2	10	10	10	1	N/A
Molars*	N/A	N/A	N/A	N/A	N/A	N/A

\*Extrusive and molar movements are allowable with standard, Daytime Aligners, however, for the purposes of this study, they will not be allowed.

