#### 8.2 Enrollment

- 8.2.1 Subjects who meet the inclusion and exclusion criteria defined above are eligible to participate in this clinical study.
- 8.2.2 Eligible subjects who agree to participate in this study and meet the eligibility criteria will be informed that their case has been accepted into the study and they are eligible to participate.
- 8.2.3 Once a subject has been enrolled, the order will be placed in the Byte system and a treatment plan is created by the Byte digital lab, using the digital impression received and FDA cleared treatment planning software (refer to K230199), to stage the subject's orthodontic treatment.
- 8.2.4 Subjects will be assigned a unique subject identification number randomly generated by the ERP system. This number will be used as the primary identifier on all study related documents. In addition subject will receive a subject Id when enrolled in the study. Subject IDs are unique to each individual subject and cannot be changed.
- 8.2.5 All enrolled subjects will be documented in the Screening Log.

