# 8.3 Study Schedule

Visit	Screening visit	Enrollment visit	Treatment start visit (Ts)	Follow-up visits (Tx - e.g. T1, T2 etc.)	Final visit (T F )
Timepoint			Day 0	T s + every 4-6 weeks during a 2-8 months period	Ts + 8 months
Informed Consent	Х				
Subject eligibility	Х	X4			
Demography	Х				
Medical history 	Х				
Concomitant medications	Х		Х	х	Х
Oral examination	Х				
X-ray 	Х				Х
Clinical photography3	Х			Х	Х
Intraoral scan	Х				Х
Intraoral refinement scan				X5	
Treatment plan (.stl- file) 		Х			
Subject questionnaire				Х	Х
Investigator questionnaire					Х
Aligners provided			Х	Х	
Aligner instructions to subject			Х		
AE/DD collection			Х	Х	Х

 Relevant medical conditions.

 Treatment screening X-ray and Treatment final X-ray (e.g. (PAN, CBCT, CEPH, and/or FMX).

 Intraoral and extraoral photographs.

 Treatment plan generated through Byte portal (final eligibility verification).

 Refinement scan only applicable if deemed needed by the investigtor.

- 8.3.1 Once aligners are manufacturered, the first fifteen (15) aligner stages will be provided to the Investigator. Additional aligner stages in sets up to fifteen (15) are provided to the Investigator to continue treatment after completion of the first fifteen (15) sets.
- 8.3.2 The Investigator will provide the subject with aligners at treatment start and at monthly check-ins with the Investigator at clinic visits.
- 8.3.3 Once the aligner trays are received by the subject, they can start their treatment. The date the aligners are received will be recorded as the start date of each subject's participation (TS). The initial visit worksheet must be completed at this time.
- 8.3.4 The subject visits will be performed monthly (every 4-6 weeks). The Investigator will review the subject's treatment progress, confirm treatment plan and follow-up on any safety events. A visit worksheet must be completed at each visit (T1, T2, T3, etc.).

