#### 12.2 Data Analysis

- 12.2.1 The Sponsor and Investigators are not blinded to the study data during the conduct of the trial, and may at periodic intervals analyze the data to assess study progress.
- 12.2.2 If nothing else is stated, descriptive statistics will be given for each variable in the clinical study and p-values may be complemented by confidence intervals as appropriate. When using the terminology descriptive statistics, it is meant that the number of subjects (N), mean, median, standard deviation (Sd), minimum (Min) and maximum (Max) values will be presented for continuous data and frequencies and percentages for categorical data.

- 12.2.3 All tooth movement data analyses will be performed using 3Shape Ortho System (K152086).
- 12.2.4 Three .stl files from each subject would be used for the analysis:
  - A pre-treatment STL file (TS) would be generated by scanning subject's pre-treatment intraoral scan taken before the start of treatment.
  - A planned or programmed STL (TP) file would be obtained from Archform Orthodontic Software System (K213916) after planned or programmed tooth movements have been made based on the treatment plan finalized by the digital lab and study Investigators.
  - The actual post-treatment STL file (TF) would be generated by scanning subject's post-treatment intraoral scan at the end of treatment.
- 12.2.5 Each STL file would convert into a Digital Study Model within the 3Shape Ortho System software to standardize the analysis.
- 12.2.6 Each DSM would be segmented using the "auto segmentation tool" of the software to demarcate each tooth separately.
- 12.2.7 This would be followed by Peer Assessment Rating (PAR) index to measure orthodontic treatment need and outcome (Richmond, 1992). This would be done using the built-in weighted PAR analysis tool of 3Shape Ortho System software. The PAR index will be performed by an external evaluator.
- 12.2.8 The weightage for each component of the PAR index would be set as: maxillary and mandibular anterior segment alignment x 1; buccal occlusion x 1; overjet x 6; overbite x 2; centerline x 4; following the ABO guidelines. The weighted PAR scores for each DSM would be compared as follows:

The PAR Score values for  $T_S$ ,  $T_P$ , and  $T_F$  will be transferred to the eCRF and the following will be calculated:

- Planned percentage reduction in PAR Score (Planned Improvement of Malocclusion [PIM]) = PAR Score TS- PAR Score TP / PAR Score TS \* 100

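### Final eligibility is decided on a treatment plan that, as written, is staged after enrollment and so implies a known arm; this permits differential exclusion after assignment

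*Combined protocol and SAP*

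**What the plan says.** Four places in the protocol set the order of events.

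- **8.1.7 (under Screening).** "Once the treatment plan is created, the Byte+ account manager will ensure that the subject's prescribed tooth movements are within the constraints and criteria" set by the inclusion and exclusion lists. If they are not, the digital lab tells the Investigator why, and "the Investigator in turn shall notify the subject and withdraw them from the study". Such a subject is not left untreated: "they can continue with their orthodontic treatment with Daytime aligners outside of the confines of this clinical study".
- **8.2.3 (under Enrollment).** The plan comes from the lab and follows the order: "Once a subject has been enrolled, the order will be placed in the Byte system and a treatment plan is created by the Byte digital" [...]. The stated purpose of that plan is to stage the orthodontic treatment.
- **8.3, schedule footnote 4.** The plan is entered at the enrollment visit and described as "Treatment plan generated through Byte portal (final eligibility verification").
- **6.1, planning constraints.** The two arms have different per-aligner limits for translation and rotation. Limits per aligner for torque, tip and intrusion are equal, and so are all total limits per treatment plan. Extrusive and molar movements are barred in both arms; for Nighttime, "Movements of molar teeth are not in the treatment plans for these aligners".

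Two further passages bear on independence. Section 2.2.2 names the companies the study serves as "Straight Smile (doing business as Byte) and Dentsply Sirona", so the account manager and digital lab belong to an interested party. Section 12.2.1 says "The Sponsor and Investigators are not blinded to the study data during the conduct of the trial". No section describes how, when or by whom the arm is assigned, or any step that keeps the arm from those who check the plan.

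**The concern.** An eligibility decision should be closed before the arm is known. Here the decision that counts comes last, is taken on a plan made by the lab of an interested company, and leads to removal. If the arm is known by then, the same borderline case can be kept in one arm and withdrawn from the other. Randomization does not repair this, because the loss happens after assignment.

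The stake is the comparability of the arms. The synopsis defines effectiveness as showing no statistically significant difference from Daytime. If harder cases left the Nighttime arm more readily, a real Nighttime deficit would be partly hidden, which favours that conclusion.

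The lost subjects cannot be recovered in the analysis. Withdrawn before aligners are delivered, they have a baseline scan and perhaps a plan, but no final scan, so neither the actual improvement nor the accuracy percentage in 9.3.1 can be computed. Section 16.4.3 keeps the data of withdrawn subjects who completed part of the trial, but it cannot supply a missing final scan.

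**Working it through.** **1. Order of steps.** Reading 8.2.3, footnote 4 and 8.1.7 together gives: enroll, place order, lab creates the plan to stage treatment, final verification, withdrawal if it fails. Section 8.1.7 sits under Screening, before Enrollment, yet needs a plan that 8.2.3 creates only after enrollment. The two are not reconciled.

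**2. Does a staged plan need the arm?** Stages = total limit / per-aligner limit, rounded up (6.1).

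- Incisor translation 5 mm: Nighttime 5/0.25 = 20; Daytime 5/0.3 = 16.7, so 17.
- Incisor rotation 45 degrees: Nighttime 45/1.6 = 28.1, so 29; Daytime 45/2 = 22.5, so 23.
- Incisor torque 25 degrees: 25/1 = 25 in both.

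Stage counts differ for translation and rotation, so a plan staged to its own limits implies the arm.

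**3. Do the written limits remove cases from one arm?** No. The lists in 5.1 and 5.2 apply to both arms, and the totals in 6.1 are identical. A smaller step adds trays; it does not make a case ineligible. Time is the only other arm-specific route: at 2 weeks per tray, a 5 mm incisor translation takes 20 x 2 = 40 weeks Nighttime and 17 x 2 = 34 weeks Daytime, against about 34.8 weeks in the 8-month planned maximum (4.3.3). At 1 week per tray the longest case takes 29 weeks and fits in both arms. The 8-month maximum is not an eligibility criterion, so this is a side remark. What remains is discretion: whether a case is planned with extrusive movement or molar or posterior correction (5.1, items 5 and 7) depends partly on the planner.

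**4. The plan's own sample size.** Difference 1, SD 1, two-sided 5%, power 90% (12.1.2). The two-sample t-test needs 22.02, rounded up to 23 per arm, with power 0.912 at 23. The stated 23 is reproduced. With the planned Wilcoxon test and normal data, simulated power at 23 is about 0.89-0.90.

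**5. Size under assumed one-sided removal.** The protocol gives neither the share removed nor the link between difficulty and outcome, so both are assumed. Let f be the hardest fraction removed from Nighttime only, and r the correlation between difficulty and poorer outcome. The Nighttime mean rises by

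shift = r x phi(z) / (1 - f), where z is the upper-f normal quantile.

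For f = 0.1: 0.1755/0.9 = 0.195, times r. For f = 0.2: 0.2800/0.8 = 0.350, times r.

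Rejection rates are from 40,000 simulated trials per setting (two-sided Wilcoxon, control N(0,1)):

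| f | r | shift (SD) | power, true 1-SD deficit, n=23 | same, n=50 | rejection, no true difference, n=23 | same, n=50 |
|---|---|---|---|---|---|---|
| 0 | - | 0 | 0.893 | 0.997 | 0.047 | 0.049 |
| 0.1 | 0.3 | 0.058 | 0.863 | 0.996 | 0.051 | 0.057 |
| 0.1 | 0.5 | 0.097 | 0.838 | 0.994 | 0.059 | 0.073 |
| 0.1 | 0.7 | 0.136 | 0.823 | 0.991 | 0.070 | 0.098 |
| 0.2 | 0.3 | 0.105 | 0.827 | 0.992 | 0.060 | 0.083 |
| 0.2 | 0.5 | 0.175 | 0.777 | 0.983 | 0.085 | 0.134 |
| 0.2 | 0.7 | 0.245 | 0.730 | 0.972 | 0.123 | 0.228 |

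**The case against.** The strongest reply is that the protocol never says the arm is known at the check. Section 8.1.7 is a screening step, 8.2.2 tells eligible subjects that their case has been accepted, and the synopsis flowchart, which might show the order, is not legible in the text available. This stands as far as it goes: arm timing is inferred from the staging purpose in 8.2.3, not stated. It does not remove the point, because 8.1.7 needs a plan that 8.2.3 makes only after enrollment. If another order is intended, the same passages must be changed to say so.

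A reader might go further and infer that the procedure breaks allocation concealment under any method. The documents do not support that. No concealment procedure is described that could be broken, and assignment after a check of the end position would keep it intact. The exact fault is possible exclusion after assignment.

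A reader might also infer that the tighter Nighttime limits themselves screen out hard cases. They do not (step 3), and the bar on molar movement is common to both arms. Nor do the documents show that anyone would use the discretion selectively.

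Other replies have partial force:

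- The check in 8.1.7 concerns tooth movements, so the exclusion for interproximal reduction or attachments (5.2, item 8) may not fall within it.
- The Investigator screens first (8.1.1), finalizes the plan with the lab (12.2.4) and carries out the withdrawal. This is a second pair of eyes, but no provision keeps the arm from the Investigator either.
- Section 12.2.1 concerns study data during conduct. It does not by itself show that the account manager knows the arm at planning.
- The screening log (5.3) and the recorded withdrawal reason (16.4.4) leave a trace, but no report by arm is required.
- The power loss is calculated at the minimum of 23 evaluable per arm, with all removal from one side. At 50 per arm it is slight.

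**Conclusion.** The point holds as a weakness in the order of steps. Followed as written, the protocol permits differential exclusion after assignment, by staff of an interested company together with the Investigator, with or without randomization. It does not show that such exclusion would occur.

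The size cannot be derived from the documents. Under wholly one-sided removal of the hardest 10-20% from Nighttime and a correlation of 0.3-0.7, the group difference shifts by about 0.06-0.25 SD in favour of Nighttime. At 23 per arm, power to see a true 1-SD deficit falls from about 0.90 to between 0.86 and 0.73; at 50 per arm it stays at 0.97 or above. Removal balanced across the arms would give no such shift.

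The direction also depends on the truth. With a real Nighttime deficit, the removal helps a finding of no difference. With no true difference, it raises false rejections to 5-12% at 23 per arm and 6-23% at 50, which works against the sponsor's aim. In both cases the comparison is biased.

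Confidence is moderate, because the arm timing is inferred. The change is worth making because it is cheap and data collected later cannot do the same job.

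**What to change.** Reconcile 8.1.7, 8.2.3 and footnote 4 of the schedule so that they give one sequence:

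1. The lab prepares an unstaged set-up showing the end position only, with no arm on the file. The account manager and Investigator decide final eligibility on it, and the decision and reason are time-stamped in the eCRF. This is feasible because the criteria and the total limits in 6.1 are identical in both arms.
2. Only then is the arm assigned or released, the order placed, and the plan staged to that arm's per-aligner limits.
3. Any later withdrawal for ineligibility is limited to a documented error and is reported by arm.

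The method of assignment also has to be stated for step 2 to work; the protocol is silent on it at present.

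The cost is protocol wording and a workflow change in the existing ordering and data-capture systems. The lab handles each case in two steps, and the order waits for the eligibility sign-off. No extra visits or subjects are needed, and no eligibility criterion or treatment limit changes.

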#### 8.2 Enrollment

- 8.2.1 Subjects who meet the inclusion and exclusion criteria defined above are eligible to participate in this clinical study.
- 8.2.2 Eligible subjects who agree to participate in this study and meet the eligibility criteria will be informed that their case has been accepted into the study and they are eligible to participate.
- 8.2.3 Once a subject has been enrolled, the order will be placed in the Byte system and a treatment plan is created by the Byte digital lab, using the digital impression received and FDA cleared treatment planning software (refer to K230199), to stage the subject's orthodontic treatment.
- 8.2.4 Subjects will be assigned a unique subject identification number randomly generated by the ERP system. This number will be used as the primary identifier on all study related documents. In addition subject will receive a subject Id when enrolled in the study. Subject IDs are unique to each individual subject and cannot be changed.
- 8.2.5 All enrolled subjects will be documented in the Screening Log.

